The Et Control feature is indicated for adult patients, 18 years of age and older. For use of the optional Et Control feature, the patient's nominal measured breath rate must be between 8 and 35 breaths/minute and the patient must be able to safely be exposed to 100% oxygen for up to 2 minutes. The optional Et Control feature is only available using Isoflurane, Desflurane, and Sevoflurane. Et Control can be used with Air or N2O as balance gases. Et Control cannot be used during a switch in inhaled agents. In these situations, the clinician is forced out of Et Control during the agent switch over period and is not allowed back into Et control until the previous drug concentration is less than 0.25 minimum alveolar concentration (MAC) (approximately 1.5 %v/v Desflurane, 0.53 %v/v Sevoflurane, or 0.29 %v/v Isoflurane) and is therefore washed out of the system.

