### 2.1.3 Additional Information Regarding the Investigational Device

#### 2.1.3.1 Manufacturer:

Datex-Ohmeda Inc.

 Agent specific %v/v values representing 1 MAC are based on the agent specific product labeling for the following representative age groups: Desflurane 6.0 %v/v age 45, Sevoflurane 2.1 %v/v age 40, Isoflurane 1.15 %v/v age 44 +/- 7.

**Study Title:** Multi-site Anesthesia randomized controlled Study of End tidal control (Et Control) compared to conventional anesthesia Results (MASTER-Anesthesia Trial)  
**Study No:** 123.07-2015-GES-0002

GE Healthcare

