### 8.1.2 Statistical Methods Overview

Data collected in this study will be presented using summary tables, data listings and graphs. Study endpoints and parameters will be summarized using descriptive statistics.

The descriptive statistics for continuous variables will include mean, standard deviation, median, Q1 and Q3, minimum, maximum, and sample size. Categorical variables will be described with counts, percentages, and sample size.

For comparison (between arms or against null values), categorical variables will be tested using appropriate contingency table analyses (exact or chi-square approximations), and continuous variables will be tested using Student's t-test or non-parametric methods, depending on variable distribution. P-values will be presented to three decimal places and p-values less than .001 will be presented as '<.001.'

**Study Title:** Multi-site Anesthesia randomized controlled Study of End tidal control (Et Control) compared to conventional anesthesia Results (MASTER-Anesthesia Trial)  
**Study No:** 123.07-2015-GES-0002

GE Healthcare

Subjects using different anesthetic agents will be pooled for analysis per the arm they are randomized. Separate analysis may be performed by anesthetic agent when pooling data across anesthetic agents is not appropriate.

No imputation will be performed for missing data unless specified otherwise.

A data extraction algorithm is used to identify periods of end tidal concentration measurement stability following setting changes (i.e. Steady States) during a case, as well as to measure response times, settling times, and overshoot amounts from these steady states in order to compare across arms. The extraction algorithm is not part of the statistical analysis, but provides the above-mentioned endpoints. (See Appendix 2 – Extraction algorithm for more information on the extraction algorithm.)

There will be two scenarios in defining a step change and steady state when performing the data extraction: 1) *using the data extraction algorithm to determine the desired end-tidal concentrations of anesthetic agent and oxygen for both arms* (See Appendix 2 – Extraction algorithm for more information on the extraction algorithm); 2) *using the clinicians recorded end tidal target values of anesthetic agent and oxygen for the Control arm, and the set target value for the Et Control arm.*

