#### 8.1.4.2 Agent Usage

The agent usage will be compared between the two arms separately for each agent for the duration from induction to end of anesthesia. Usage of anesthetic agents will be normalized so that usage of different anesthetic agents can be pooled in analysis. It is intended to make claims on saving of anesthetic agent usage. The normalized anesthetic agent usage will be compared using t-test at two-sided alpha 0.05 between the Et Control Arm and Control Arm only if non-inferiority is concluded on primary endpoints; thus, no multiplicity adjustment is needed using the fixed sequence approach. The hypothesis to be tested on anesthetic agent usage is:

$$H_0: \mu_{\text{et}} - \mu_{\text{con}} = 0 \text{ vs } H_1: \mu_{\text{et}} - \mu_{\text{con}} \neq 0$$

where  $\mu_{\text{et}}$  is the average normalized anesthetic agent usage of the Et Control arm, and  $\mu_{\text{con}}$  is the average normalized anesthetic agent usage of the control arm.

Agent usage will also be analyzed for each agent.

Additional analysis on agent usage will be performed for the first 10 minutes after induction.

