### 8.1.5 Et Control Accuracy

To assess the accuracy of Et Control in maintaining the target EtAA and EtO2 concentrations for each steady state, both mean absolute difference and mean percent difference between measured Et concentrations of AA and the setting values will be calculated, and the mean differences will be summarized for all steady states using descriptive statistics and 95% confidence intervals for each anesthetic agent and overall. The same accuracy analysis will be performed for EtO2. The mean differences will also be plotted against the setting values to assess consistency across the concentration range for each anesthetic agent. Percent of time duration in a steady state will also be assessed; when the percent difference exceeds 5%, 10%, and 15% of the setting values.

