### 8.1.9 Other Analysis

Delivered EtAA and EtO2 concentrations will be summarized by anesthetic agent and overall for both arms to demonstrate the comparability in anesthesia practice.

Delivered EtAA and EtO2 concentrations and their deviations to set values for the duration of +/- 10 minutes of an AE will be summarized for both arms.

Oxygen (O2) usage from induction to the end of surgery will be summarized and compared between the two study arms using t-test.

Post-anesthesia discharge time will be summarized and compared between the two study arms using t-test. Post- anesthesia discharge time is defined as OR discharge (patient disconnected from the anesthesia machine) to discharge time from the PACU (*defined as the time patient meets criteria to discharge from PACU*).

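### The overall EtAA summary (8.1.9) and the overall mean absolute difference (8.1.5) pool raw %v/v across three agents with very different 1 MAC values, so both depend heavily on agent mix

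*Combined protocol and SAP*

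**What the plan says.** Section 8.1.9 plans that delivered EtAA and EtO2 be "summarized by anesthetic agent and overall for both arms to demonstrate the comparability in anesthesia practice". It then plans a second summary, for both arms, of the concentrations and their deviations from set values within 10 minutes either side of an adverse event. No split by agent is stated for that one.

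Section 8.1.5, which concerns the Et Control arm only, plans that "both mean absolute difference and mean percent difference between measured Et concentrations of AA and the setting values will be calculated". The results are to be "summarized for all steady states using descriptive statistics and 95% confidence intervals for each anesthetic agent and overall".

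Neither section rescales EtAA before the overall figure is formed. Footnote 1 in section 2.1.3 gives the 1 MAC values as "Desflurane 6.0 %v/v age 45, Sevoflurane 2.1 %v/v age 40, Isoflurane 1.15 %v/v age 44 +/- 7". For agent usage the plan does rescale: "Usage of anesthetic agents will be normalized so that usage of different anesthetic agents can be pooled in analysis" (section 8.1.4.2). The general rule in section 8.1.2 is to pool agents within arm, with the option that "Separate analysis may be performed by anesthetic agent when pooling data across anesthetic agents is not appropriate".

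Randomization is stratified by investigator, hypertension status and ASA status (section 6.1). The only stated constraint on agent mix is a target of at least 15 subjects per agent per arm, out of about 124 (section 5.1).

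**The concern.** A given %v/v means a different thing for each agent: 1 MAC of desflurane is 5.2 times 1 MAC of isoflurane. A mean of raw EtAA over all three agents therefore mixes how deeply patients were anesthetized with which agents they received. The plan recognizes this elsewhere. It normalizes usage before pooling, and it sets agent-specific limits in the primary endpoint (0.6, 0.2 and 0.1 %v/v, or about 0.10, 0.095 and 0.087 MAC).

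The overall EtAA summary has a stated purpose, which is to show that anesthesia practice was comparable in the two arms. A reader weighing a saving in agent would look there to see whether one arm simply ran lighter. On the raw scale that figure can differ between arms run at the same depth, or look alike when depth differs. The overall mean absolute difference has a related weakness: its size depends on the agents that supplied the steady states as well as on how well the device held its target.

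**Working it through.** **Inputs.** 1 MAC = 6.0 (Des), 2.1 (Sev) and 1.15 (Iso) %v/v, from footnote 1 in section 2.1.3. About 124 subjects per arm and a target of at least 15 per agent per arm, from section 5.1. The documents give no expected agent mix, so every mix below is an assumption.

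**The documents' own conversion.** The device description in section 2.1 gives 0.25 MAC as "approximately 1.5 %v/v Desflurane, 0.53 %v/v Sevoflurane, or 0.29 %v/v Isoflurane". From the footnote, 0.25 × 6.0 = 1.5, 0.25 × 2.1 = 0.525 and 0.25 × 1.15 = 0.2875. These round to the stated figures, so the plan already contains a consistent common scale. The ratios at 1 MAC are 6.0/1.15 = 5.2, 6.0/2.1 = 2.9 and 2.1/1.15 = 1.8.

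**Range of the overall mean at identical depth.** Put every subject at exactly 1 MAC. Overall EtAA = (6.0 n_Des + 2.1 n_Sev + 1.15 n_Iso)/124. With two agents at 15, the third has 124 − 30 = 94.

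- 94/15/15: (564 + 31.5 + 17.25)/124 = 4.94 %v/v
- 15/94/15: (90 + 197.4 + 17.25)/124 = 2.46 %v/v
- 15/15/94: (90 + 31.5 + 108.1)/124 = 1.85 %v/v

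This 2.7-fold range bounds what the target permits. It is not a forecast of the gap between two randomized arms.

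**Chance imbalance between arms.** Treat agent as independent of the stratification factors. With shares p and 1 MAC values v, the mean is m = Σpv, the between-agent variance is V = Σpv² − m², and the 95% range of the arm difference is ±1.96 √(2V/124).

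- 30/58/12%: m = 3.156, V = 13.517 − 9.960 = 3.56, range ±0.47 %v/v (15% of the mean)
- 40/48/12%: m = 3.546, V = 16.676 − 12.574 = 4.10, range ±0.50 %v/v (14% of the mean)
- Wider set of mixes, from 12/76/12% through equal thirds to 12/12/76%: ±0.34 to ±0.52 %v/v (14–21% of the mean)

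**A reversal.** An arm at 1.10 MAC with mix 20/74/30 reads 1.10 × 309.9/124 = 2.75 %v/v. An arm at 1.00 MAC with mix 30/64/30 reads 348.9/124 = 2.81. The deeper arm has the lower overall mean.

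**Absolute accuracy.** Let the error be 3% of 1 MAC for every agent. If steady states were shared as 94/15/15, 15/94/15 or 15/15/94, the overall mean absolute difference would read 0.148, 0.074 or 0.056 %v/v. Section 8.1.5 summarizes steady states and the 15-per-agent target counts subjects, so these figures only illustrate the dependence.

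**After rescaling.** Dividing by the agent's 1 MAC value gives 1.00 for every arm held at 1 MAC, whatever the mix. In the reversal example the arms read 1.10 and 1.00. The 3% error reads 0.03 MAC for every mix.

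**The case against.** Most of the case on the other side stands, and it limits the point.

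- A reader might infer that section 8.1.9 formally compares overall EtAA between arms. It does not. It plans a summary, while oxygen usage and post-anesthesia discharge time in the same section are explicitly compared by t-test. No test, interval or decision rule attaches to overall EtAA.
- Sound versions of the same information are already planned. EtAA is also shown by agent. Section 8.1.5 also gives the percent difference and the percent of time beyond 5%, 10% and 15% of the setting, which are unit-free and pool properly. A difference in depth blurred in the overall row could still appear in the by-agent rows.
- A reader might infer that the agent-saving claim or the primary result is compromised. The documents do not support that. The primary limits are agent-specific, the usage test is gated on primary non-inferiority and not on EtAA, and usage is also analyzed by agent.
- A reader might suppose that the raw overall figure is needed for precision because some by-agent tables may be small. Under the two mixes above and an assumed within-agent CV of 10–20%, the half-width of the overall arm difference is 14.5–16% of the mean. It is 4–9% for desflurane, 3–7% for sevoflurane and 7–14% for isoflurane at 15 per arm. Raw pooling loses precision.
- The chance ranges ignore stratification by investigator. To the extent that agent choice follows investigator, imbalance shrinks. Against that, clinicians are unblinded and I found no statement that the agent is fixed before randomization, so imbalance need not be purely chance.
- Accuracy is reported for Et Control only, so no arm comparison is distorted there.

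The option of separate analysis in section 8.1.2 is permissive and does not alter how the overall figures are formed. What remains is that two planned pooled figures, one of them with a stated purpose, are confounded with agent mix as written.

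**Conclusion.** The point holds for the overall EtAA concentration in section 8.1.9 and the overall mean absolute difference in section 8.1.5. The adverse-event window summary in 8.1.9 shares the defect if it is pooled across agents. At identical depth the overall mean could be 1.85 to 4.94 %v/v under the 15-per-agent target. With mixes of 30–40% Des, 48–58% Sev and 12% Iso, chance could move the arm difference by about ±0.5 %v/v. The first range rests only on the protocol's MAC values, the target and 124 per arm. The second also rests on assumed mixes and on agent being independent of investigator.

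It would go too far to say that these figures carry no information on depth or accuracy: they reflect both, mixed with agent choice. Pooling EtO2 across agents raises no such problem. This is a worthwhile correction to supportive reporting and does not threaten the trial's conclusions.

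**What to change.** In sections 8.1.5 and 8.1.9, divide EtAA and its absolute difference from the setting by the agent's 1 MAC value in footnote 1 (6.0, 2.1 or 1.15 %v/v) before any summary pooled across agents, including the summary around adverse events. Report the between-arm difference in overall EtAA in MAC multiples with a 95% CI. Keep %v/v for the by-agent tables, and tabulate agent mix by arm.

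The cost is a few lines of SAP wording, one derived variable and one small table. No new data are needed, and the sample size and primary analysis do not change. Precision improves: with a common mean of 1 MAC and the same assumed CV of 10–20%, the half-width of the overall arm difference becomes 1.96 × CV × √(2/124), or 2.5–5.0% of the mean.

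There is one small downside. The footnote values are for representative ages of about 40 to 45, while the trial enrolls adults from 18 with no upper age limit. The rescaled figure is a common scale across agents and not an age-adjusted measure of depth, and the table should say so.

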#### 1.1.2 Principles of Minimum Alveolar Concentration

[figure not shown]

Figure 1-1: Yasuda Anesthesia Analgesia 1991

Minimum Alveolar Concentration (MAC) is used to compare the potency of inhaled anesthetic vapors. Inhaled anesthetic agents (isoflurane, desflurane, and sevoflurane) are dosed according to MAC that is measured by the end-tidal concentrations. In volunteer subjects ventilated in a non-rebreathing system, Yasuda showed that after 30 minutes there remains

**Study Title:** Multi-site Anesthesia randomized controlled Study of End tidal control (Et Control) compared to conventional anesthesia Results (MASTER-Anesthesia Trial)  
**Study No:** 123.07-2015-GE5-0002

GE Healthcare

a difference between the alveolar and inspired anesthetic concentrations. The differences were illustrated by the FA/FI ratio of the alveolar (measured as the expired concentration) to the inspired concentrations of less than 1. For desflurane, sevoflurane and isoflurane these ratios were 0.91, 0.85, and 0.73. These differences are related to rate of patient uptake and distribution of anesthetic agent and its solubility.

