### 6.1.1 Investigational Et Control Arm

The subjects assigned to this group are induced and their airway secured based on each investigator's conventional intravenous induction and intubation practice. Machine log data are collected when the investigator initiates the start of anesthesia case on the Aisys CS.

The investigator will initiate Et Control after the airway is secured (intubation) and mechanical ventilation is initiated. Machine log data is collected when the investigator initiates the start of anesthesia case on the Aisys CS. Adjustments to the anesthesia machine settings, discontinuation of use of the investigational Et Control option, and changes to treatment are based upon clinician judgment for the wellbeing of the subject. This protocol does not in any way instruct the clinician to make any dosage changes or adjustments for study purposes. All dosage decisions are based on their normal clinical practice.

Aisys CS machine log data collection will end when an "end case" is confirmed on the Aisys CS at the end of the anesthesia case. Evaluable Aisys CS data ends when the patient is finally disconnected from the Aisys CS breathing system.

The clinician must continuously monitor measured inspired and end tidal oxygen and anesthetic concentrations to assess individual responses and compare to the target concentrations.

The clinician must maintain adequate ventilation to deliver appropriate oxygen and anesthetic agent to the patient. Et Control does not adjust ventilator parameters.

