### 6.3.2 Operative Procedure Data Collection (Induction/Intubation, Maintenance, and Emergence)

The following information will be collected from each subject case.

- ◆ Collect the following data from the departmental electronic medical record (EMR) from induction through emergence phase:

**NOTE:** *Collection of vital signs shall be made at a minimum of every 2.5 minutes for the first 2 hours of each case, and at a minimum of every 5 minutes thereafter through the emergence phase. If the subject becomes unstable, the clinician shall revert to collecting the vital signs at a minimum of every 2.5 minutes, and shall record the reason for change in the collection of vital signs and any adverse events that may occur. Once the subject returns to a stable state, the clinician shall collect the vital signs at a minimum of every 5 minutes.*

1. Heart Rate
  2. Blood Pressure (systolic and diastolic)
  3. Mean Arterial Pressure (MAP)
  4. Peripheral Capillary Oxygen Saturation (SpO2)
- ◆ Record the following data on the eCRFs throughout the study:
    1. Concomitant Medications: Intravenous medications [name, dose, time administered, time stopped, and rate (if applicable); including intravenous anesthetic agents used prior to intubation] administered from pre-OP through emergence phase
    2. Vasoactive medications: (e.g., Ephedrine, Epinephrine, Dopamine, Norepinephrine, Phenylephrine, etc.) including name, dose and unit, rate, time administered, time stopped, and reason for dose (prophylactic, hypotension, anesthetic overdose, hypovolemia, depressed cardiac output, depressed systemic vascular resistance, dose decrease or other) – administered from induction to emergence phase
    3. Anesthetic agents used prior to intubation (*Note: Record inhaled and intravenous anesthetic agent used prior to intubation. Intravenous anesthetic agent should be recorded in the Intravenous Medication During Study eCRF.*)
    4. Time of induction
    5. Time of intubation
    6. Operative positioning (*record the primary operating position*)
    7. Incision time

**Study Title:** Multi-site Anesthesia randomized controlled Study of End tidal control (Et Control) compared to conventional anesthesia Results (MASTER-Anesthesia Trial)  
**Study No:** 123.07-2015-GE5-0002

GE Healthcare

8. Estimated blood loss
  9. End time of surgery (*often defined as the procedure end time, last stitch, or placement of the last bandage*)

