**Table 10-1 – Anticipated Adverse Events and Device Effects**

Event	Machine Failure	General Anesthesia	Aisys CS 	Et Control
Hypoxia	Insufficient oxygen delivery	x	x	x
	Incorrect oxygen concentration of fresh gas flow	x	x	x
	Insufficient ventilation	x	x	x
Hyperoxia	Excessive oxygen delivery	x	x	x
Cardiac Arrest	Incorrect anesthetic agent delivery	x	x	x
Intra-operative Awareness	Insufficient AA delivery	x	x	x
Hypertension	Insufficient anesthetic agent delivery	x	x	x
Hypotension	Excessive anesthetic agent delivery	x	x	x
Airway Fire	Electro-cautery in airway with high O 2	x	x	x

Adverse event assessment will be conducted from the time the subject provided consent to the end of the subject's participation in the study.

There is always a chance of unexpected risks. Throughout the study, the Sponsor will evaluate and update safety information in study documents.

**Study Title:** Multi-site Anesthesia randomized controlled Study of End tidal control (Et Control) compared to conventional anesthesia Results (MASTER-Anesthesia Trial)  
**Study No:** 123.07-2015-GE5-0002

GE Healthcare

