## 10.2 Adverse Event Definitions

**Adverse Event (AE):** As defined by EN ISO 14155-2011: any untoward medical occurrence, unintended disease or injury, or untoward clinical signs (including abnormal laboratory findings) in subjects, users or other persons, whether or not related to the investigational medical device.

**NOTE:** *This definition includes events related to the investigational medical device or the comparator. This definition includes events related to the procedures involved.*

Given the frequency at which physiological changes occur during the course of general anesthesia, the following definitions for changes in blood pressure, heart rate, and oxygenation will be used to determine adverse event reporting. If any of the parameters reach the below thresholds they shall be reported to the Sponsor as adverse events.

- (1) **Non-Invasive Blood pressure (NIBP):** defined as having the systolic blood pressure (SBP) reading < 70 mmHg or > 160 mmHg or mean arterial pressure (MAP) of < 55 mmHg or > 120 mmHg for > 5 minutes.
- (2) **Peripheral Capillary Oxygen Saturation (SpO2):** defined as having a value less than 90% for more than 5 minutes.
- (3) **Heart rate:** defined as the heart rate < 45bpm or > 110bpm for more than 5 minutes.

Additional adverse events related to physiological changes can be reported at the clinician's discretion.

**Serious Adverse Event (SAE):** As defined by EN ISO 14155-2011: an adverse event that

- a. led to death;
- b. led to a serious deterioration in the health of the subject, that either resulted in:
  - (1) a life-threatening illness or injury, or
  - (2) a permanent impairment of a body structure or a body function, or
  - (3) in-patient or prolonged hospitalization, or
  - (4) medical or surgical intervention to prevent life-threatening illness or injury or permanent impairment to body structure or a body function;
- c. led to fetal distress, fetal death, or a congenital abnormality or birth defect.

**NOTE:** *Planned hospitalization for a pre-existing condition, or a procedure required by the Clinical Investigation Plan (clinical protocol), without serious deterioration in health, is not considered a serious adverse event.*

**Anticipated Adverse Device Effect:** Any adverse event and/or reaction, the specificity or severity of which is consistent with the IRB approved informed consent, protocol, investigator brochure, or product labeling.

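### Section 8.1.9 summarises gas delivery over one window from 10 minutes before to 10 minutes after an adverse event, so possible cause is mixed with the clinician's response

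*Combined protocol and SAP*

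**What the plan says.** Section 8.1.9 (Other Analysis) covers delivered EtAA and EtO2 "concentrations and their deviations to set values", and states that these "for the duration of +/- 10 minutes of an AE will be summarized for both arms". It does not divide the window, say what the window is centred on, say whether deviations are signed or absolute, or say what the set value is in the Control Arm.

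Four other places bear on how the summary will read:

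- Section 10.2 makes threshold breaches in vital signs reportable: "If any of the parameters reach the below thresholds they shall be reported to the Sponsor as adverse events". Each carries a duration, for example "mean arterial pressure (MAP) of < 55 mmHg or > 120 mmHg for > 5 minutes".
- Section 10.3 collects an onset time for every adverse event, but Section 8.1.9 does not refer to it.
- Table 10-1 names the mechanism of interest. Against hypotension it lists "Excessive anesthetic agent delivery"; against awareness and hypertension it lists insufficient delivery.
- Section 6.1.1 leaves the reaction to the clinician: "Adjustments to the anesthesia machine settings, discontinuation of use of the investigational Et Control option, and changes to treatment are based upon clinician judgment".

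**The concern.** If over-delivery contributes to hypotension, the evidence lies in the minutes before the pressure falls. Once the event is recognised the clinician may lower the agent, so the minutes afterwards show the reaction. A summary across both periods blends two quantities that may point in opposite directions.

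The unstated anchor makes this worse. A vital-sign event needs more than 5 minutes beyond its threshold. If the window is centred on the moment the event qualifies, about half of the 10 minutes before it already lies after the first breach and may contain the response.

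At stake is the readability of a table that sets the machine log directly against adverse events. Relationship to the device is otherwise judged by an investigator who, under Section 4.2, cannot be blinded to arm.

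**Working it through.** Section 8.1.9 contains no figure to reproduce. The recomputable design figures are those in Table 8-1. By the two-sample t method they come out as stated: 105/0.85 gives 124 per arm for EtAA and 57/0.85 gives 68 for EtO2. They have no bearing on this point.

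**Illustration for delivered concentration**

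Inputs:

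- Pre-event excess over the original target: x = 0.6 %v/v sevoflurane, held for the full 10 minutes before the event. The size is borrowed from Section 11.1; the persistence is assumed.
- Speed of change: 90% reached in 78 s (Table 1-1, average EtAA response at one European site). With exponential approach, τ = (78/60)/ln 10 = 0.565 min.
- Delay L from event to reaction: 0, 2.5 or 5 minutes (assumed). The middle value matches the recording interval in Section 6.3.2: "Collection of vital signs shall be made at a minimum of every 2.5 minutes for the first 2 hours of each case".
- Level finally reached: f·x relative to the original target. f = 0 means back to target; f = -1 means as far below target as it had been above.

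The mean over the 10 minutes after the event is [xL + fx(10 - L) + (1 - f)xτ]/10; the neglected exponential tail is negligible. The mean over the whole window is the average of x and that value. For L = 0 and f = -1, the mean after the event is (-6.0 + 1.2 × 0.565)/10 = -0.532, and the whole-window mean is (0.600 - 0.532)/2 = 0.034.

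| Delay L (min) | Final level (%v/v) | Mean before | Mean after | Whole-window mean | Share of pre-event value |
|---|---|---|---|---|---|
| 0 | 0 | 0.60 | 0.034 | 0.317 | 53% |
| 0 | -0.6 | 0.60 | -0.532 | 0.034 | 6% |
| 2.5 | 0 | 0.60 | 0.184 | 0.392 | 65% |
| 2.5 | -0.6 | 0.60 | -0.232 | 0.184 | 31% |
| 5 | 0 | 0.60 | 0.334 | 0.467 | 78% |
| 5 | -0.6 | 0.60 | 0.068 | 0.334 | 56% |

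The shares do not depend on x. With x = 0.2, the whole-window mean runs from 0.011 to 0.156, again 6% to 78%. Reporting the earlier half alone returns the full 0.60 in every row.

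**Deviation from the set value in Et Control**

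Here the reference moves when the clinician lowers the target. Suppose a persistent device bias of +0.20 and a target lowered by c after 2.5 minutes. The whole-window mean deviation is then 0.20 + cτ/20. For c from 0 to 0.6 it runs from 0.200 to 0.217. A persistent bias is not cancelled. The small addition is lag after the target change, which is again response mixed with possible cause.

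**The case against.** The strongest reply is that Section 8.1.9 says only that the data will be summarised. Section 8.1.2 defines a summary of a continuous variable as mean, SD, median, quartiles, minimum and maximum, alongside listings and graphs. In the worst row above, the minimum and maximum would be close to -0.6 and +0.6. A reader might infer that a real deviation could vanish from the report; the documents do not support that. What stands is narrower: those statistics show that values spread, but not whether the high values came before or after the event, which is what the table needs to tell.

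Three other stronger readings also go too far.

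- **That device error cancels in the Et Control Arm.** The second calculation shows that it need not, because the target moves with the clinician's reaction.
- **That Control Arm deviations will be taken from the vaporizer setting, with built-in gaps of 9%, 15% and 27%.** Section 1.1.2 does say "For desflurane, sevoflurane and isoflurane these ratios were 0.91, 0.85, and 0.73". Those are alveolar-to-inspired ratios in volunteers on a non-rebreathing system, not gaps from a vaporizer setting. Sections 3.4.1 and 8.1.3 already use the clinician's recorded end-tidal target as the Control Arm reference. The term used in Section 8.1.9 is loose and should be tied to that reference, but the text does not establish a biased comparison.
- **That nothing else links adverse events to delivery.** Section 6.3.2 records reasons for vasoactive drugs, including anesthetic overdose, and Section 8.1.8 analyses them. Section 10.3 records relationship to device and agent. Section 11.1 makes sustained EtAA deviation a reason for early termination.

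It is also fair to say that the breath-by-breath log is kept, so a split could be produced later. A split chosen after the data are seen would carry less weight.

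**Conclusion.** The point holds as a cheap improvement. The single window mixes delivery that could have contributed to an adverse event with the response to it, and no other section separates them. For delivered concentrations, a whole-window mean keeps 6% to 78% of a pre-event deviation in the illustration. Partial dilution is the usual result; near-cancellation needs an immediate reaction that overshoots by as much as the original excess. A change of sign would need a larger overshoot still, and none of the cases worked here shows one.

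The range rests on assumed reaction delays, an assumed constant excess before the event, and a response time from Et Control use in a small European study. The plan gives none of these for this purpose. That the table is meant to reveal over- or under-delivery is inferred from its placement around adverse events and from Table 10-1; Section 8.1.9 states no purpose. The summary is descriptive, so the primary endpoints, the type I error and the sample size do not depend on it.

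**What to change.** Amend Section 8.1.9 before the data are seen:

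- Report -10 minutes to onset and onset to +10 minutes separately, by arm.
- Define onset as the time recorded under Section 10.3 and, for vital-sign events, as the first reading beyond the threshold. That reading is only as precise as the recording interval in Section 6.3.2. Name the threshold source: Section 10.2 and the Glossary give different lower systolic limits (70 and 75 mmHg) and must be reconciled. State how events without a clear intraoperative onset, such as awareness elicited at the 24-hour assessment, are handled.
- Use signed deviations from the end-tidal target: the set target in Et Control and, as in scenario 2 of Section 8.1.3, the clinician's recorded target in the Control Arm.
- Report by arm how many windows lack a recorded target.

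The cost is a few lines of text and one extra table. The drawback is missing Control Arm targets. Appendix 2 says that clinicians record them, but Section 6.3.2 does not list where they are captured. Section 8.3 treats the target as missing when a significant change has no recorded value, and the minutes after an adverse event are a likely place for that. Delivered concentrations need no target, so they can be shown for both halves whenever the log is complete.
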